3.1.2 Analysis Visits

Scheduled visits will be assigned to analysis visits as recorded on the case report form (CRF). Early termination visits will be assigned to analysis visits according to the following visit windows:

Analysis Visit	Target Analysis Day	Low Analysis Day	High Analysis Day
Day 1	1	NA	NA
Week 2	14	2	21
Week 4	28	22	42
Week 8	56	43	70
Safety Follow-up	84	71	

Unscheduled visits recorded on the CRF will not be re-assigned and remain labeled as unscheduled.

3.1.3 *Definition of Baseline*

Unless otherwise stated, Baseline will be defined as the last measurement prior to the first dose of study drug.

3.1.4 *Summary Statistics*

Categorical data will generally be summarized with counts and percentages of participants. The denominator used for the percentage calculation will be clearly defined. Continuous data will generally be summarized with descriptive statistics including n (number of non-missing values), mean, median, standard deviation, minimum, and maximum.

3.1.5 *Evaluation of Site Effect*

This is a multi-center study. Sites will not be pooled for any planned inferential analysis but may be pooled for subgroup analysis to assess the heterogeneity of treatment effects among pooled sites. The final pooling algorithm, if needed, will be specified before treatment unblinding and will be provided as an addendum to the SAP. Additionally, a review of by-site effects will be performed in the context of data listing review.

3.1.6 *Handling of Dropouts and Missing Data*

Date Values

In cases of incomplete dates (e.g. adverse event (AE), concomitant medication, and medical history start and/or stop dates), the missing component(s) will be assumed as the most conservative value possible. For example, if the start date is incomplete, the first day of the month will be imputed for the missing day and January will be imputed for the missing month. If a stop date is incomplete, the last day of the month will be imputed for the missing day and December will be imputed for the missing month. Incomplete start and stop dates will be listed as collected without imputation.

Date imputation will only be used for computational purposes such as treatment-emergent status. Actual data values, as they appear in the original CRFs, will be presented within the data listings.

Non-Date Values

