3.3.7 Study Drug Exposure and Compliance

Participants' exposure to randomized study medication will be summarized with descriptive statistics by treatment for the Safety Population. Days of exposure is defined as:

$$\text{Exposure (days)} = \text{date of last dose of study drug} - \text{date of first dose} + 1$$

For those who failed to provide the date of last dose of study drug, the earliest date between the end of treatment date and the date of end of study/early termination will be used.

A summary will be provided to display counts and percentages of participants in each treatment with exposure in the following categories: <4 weeks, 4 – <8 weeks, and 8+ weeks.

Summary statistics will be presented for percent overall compliance to study medication by treatment. Counts and percentages of participants will also be tabulated by groups with overall compliance < 80%, 80% to 120%, and > 120%.

The percent overall compliance to study medication will be calculated as:

$$\text{Compliance (\%)} = \frac{(\# \text{ tablets dispensed} - \# \text{ tablets returned})}{\# \text{ expected dosing days}} \times 100$$

The number of expected dosing days = (the earliest date between the end of treatment date and the date of early termination – the date of randomization + 1).

A separate listing of derived exposure and compliance will be provided for ITT Population.

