In order to maintain the overall alpha level on the primary endpoint, the hypothesis testing will be performed sequentially at the 2-sided alpha=0.05 significance level. The first comparison will be the 10 mg obicetrapib group versus placebo; if significant, comparison of the 5 mg obicetrapib group versus placebo will be performed, followed by the 2.5 mg obicetrapib group versus placebo. Hypothesis testing will proceed in this hierarchical step-down fashion until a comparison is not significant. At that point, all remaining sequential tests will be deemed not significant.

The MMRM approach will include all available assessments of percent change in LDL-C from Baseline to Day 14, Day 28, and Day 56. The model assumes the data are missing at random (MAR). If any data are missing, the model will use all information from the other time points as well as Baseline covariate values to estimate the mean treatment difference at the given time point. No imputation of missing data will be performed for the primary efficacy endpoint analysis.

In order to address the effect of intercurrent events, "While-on-Treatment Strategies" will be employed¹. For participants who are withdrawn from the study because of the use of an excluded medication and/or procedure, data occurring after the intercurrent event of excluded medications use will be excluded from the primary analysis. For participants who are withdrawn from the trial, data occurring after the intercurrent event of failure to adhere to treatment dosing will be excluded from the primary analysis. Failure to adhere to treatment dosing will be defined as study drug compliance <75% at the time of study withdrawal.

The MMRM analysis will be implemented using SAS[®] Proc Mixed. Example SAS code can be found below:

Note:

USUBJID = unique subject identifier

TREATMENT = 0 (Placebo), 1 (2.5 mg obicetrapib), 2 (5 mg obicetrapib), 3 (10 mg obicetrapib)

VISIT = Visit

BASE = Baseline value

PCHG = Percent change from Baseline

proc mixed;

class USUBJID TREATMENT VISIT;

model PCHG = TREATMENT BASE VISIT TREATMENT*VISIT / solution cl;

repeated VISIT / TYPE=UN sub=USUBJID;

lsmeans VISIT*TREATMENT / cl diffs;

run;

Values, changes from Baseline, and percent change from Baseline of LDL-C will be summarized using descriptive statistics at scheduled visits and Baseline by treatment group.

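### SAP 3.4.1 names a while-on-treatment strategy, but its exclusions do not remove LDL-C sampled after study drug has been stopped or interrupted

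*SAP*

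**What the plan says.** SAP 3.4.1 puts every available Day 14, 28 and 56 LDL-C percent change into the MMRM, without imputation and under a missing-at-random (MAR) assumption. For intercurrent events it adopts "While-on-Treatment Strategies" and gives two exclusions.

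- The first opens "For participants who are withdrawn from the study because of the use of an excluded medication and/or procedure" and removes data after that use.
- The second, also for the primary model, reads "For participants who are withdrawn from the trial, data occurring after the intercurrent event of failure to adhere to treatment dosing will be excluded". The event is then defined: "Failure to adhere to treatment dosing will be defined as study drug compliance <75% at the time of study withdrawal".

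Three other provisions decide which values reach the model.

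- SAP 3.1.2: "Early termination visits will be assigned to analysis visits according to the following visit windows", with Week 8 covering Days 43 to 70. For all other planned visits, "Scheduled visits will be assigned to analysis visits as recorded on the case report form".
- SAP 3.3.7 gives the compliance formula, tablets dispensed minus returned over expected dosing days, and sets the denominator: "The number of expected dosing days = (the earliest date between the end of treatment date and the date of early termination", less the randomization date, plus one. End of treatment date is not defined, and SAP 3.4.1 does not refer to this formula.
- Protocol Appendix A schedules a lipid profile at the ET visit but none at Visit 6, the Safety Follow-up.

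**The concern.** A while-on-treatment analysis uses outcomes observed while the participant is on drug. To deliver it, a data rule needs a date on which treatment ended or lapsed, and it must apply to everyone. The rules in SAP 3.4.1 have neither feature for stopped or interrupted drug. They are conditional on study withdrawal, although protocol 4.5 treats stopping drug and leaving the study as separate cases. The adherence event is also judged at withdrawal, so, read literally, little or no data can come after it.

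At stake is the meaning of the primary estimate. It could mix on-drug and off-drug LDL-C, and two programmers following SAP 3.1.2, 3.3.7 and 3.4.1 could analyse different Week 8 values. In a dose-finding study the size of each arm's effect matters, not only its p-value.

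**Working it through.** **Inputs.** Protocol 9.2.5 and SAP 2.2.4: 25 evaluable per arm, difference 30 points, SD 25, two-sided 0.05, 7% dropout, 27 enrolled per arm. SAP 3.1.2: Week 8 = Days 43–70. SAP 3.4.1: 75% threshold. Assumed, because the documents do not give them: the gap from last dose to ET visit, the LDL-C offset, and full dosing up to the last dose.

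**The plan's own figures.** SE = 25 × √(2/25) = 7.07 and 30/7.07 = 4.24. Two-sample t power is 98.6%, consistent with the stated >90%. 25/0.93 = 26.9, so 27 per arm and 108 in total. Both reproduce. At 27 per arm, SE = 25 × √(2/27) = 6.80 and power is 99.1%.

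**Route (a): the ET sample.** Let L be the last-dose day and E the ET day. Counted to ET, compliance is L/E. If end of treatment means last dose, SAP 3.3.7 takes the earlier date and compliance is L/L = 100%.

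| L | E | Days off drug | Counted to ET | End of treatment = last dose | Mapped to |
|---|---|---|---|---|---|
| 36 | 43 | 7 | 83.7% | 100% | Week 8 |
| 42 | 56 | 14 | 75.0% | 100% | Week 8 |
| 30 | 50 | 20 | 60.0% | 100% | Week 8 |

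The first two rows are kept under either count, because 75.0% is not below 75%. The third is kept only under the second count. The undefined end date therefore decides such cases.

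**Route (b): no withdrawal.** A participant who stops or interrupts drug, is not withdrawn and attends Visit 5 meets neither exclusion, and that value enters as recorded. Protocol 8.1.4.2 foresees interruption with possible resumption. A completer who took 28 of 56 tablets (50%) is likewise untouched.

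**Other provisions.** For stopped drug, the mITT removal rule (protocol 9.1, SAP 3.2.2) covers only the Safety Follow-up Visit, where no lipid profile is scheduled. The mITT On-Treatment Population (SAP 3.2.3) checks plasma concentration at Day 56 but is supportive, as is PP.

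**Size.** Shift = (k/27) × 30 × r, where k is the number of off-drug Week 8 values in an active arm and r the share of effect lost.

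- k = 1, r = 1: 1.11 points, difference 28.9. Power is 98.6% with SD held at 25, and 98.4% with the active-arm SD widened by the mixture to 25.6.
- k = 2, r = 1: 2.22 points, difference 27.8. The mixture SD is √(625 + (2/27)(25/27)(900)) = 26.2. Power is 98.0% (SD 25) or 97.4% (mixture SD).
- k = 2, r = 0.5: 1.11 points, difference 28.9.

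Two dropouts per arm match the planned 7% (2/27 = 7.4%). If last doses fall evenly over Days 1–55 and ET comes 7 days later, last doses on Days 36–55 give a kept Week 8 value. That is 20/55 = 36%, or 2 × 0.364 = 0.73 values, or 0.73 × 1.11 = 0.81 points at r = 1. With a 14-day gap the share is 14/55 = 25% counted to ET (0.57 points), or 27/55 = 49% if every stopper scores 100% (1.09 points).

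**The case against.** Several points on the other side stand.

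- The excluded-medication rule does have an event anchor, since data after that use are cut. The mITT sentence can also be read as removing any efficacy value after an excluded medication, withdrawn or not. A reader might infer that neither exclusion has a cut point; the SAP does not support that. This point is confined to stopped or interrupted drug.
- The SAP does contain a compliance formula. What is missing is a reference to it in 3.4.1 and a definition of its end date.
- Route (b) is probably uncommon. Protocol 4.5 asks early stoppers for a prompt ET visit and describes no later Visit 5. The interruption in 8.1.4.2 follows a confirmed, unexplained CK elevation with symptoms, and no frequency is given.
- Full return to baseline is a pessimistic assumption for samples a few days after the last dose. Some of the values counted above might fall inside any reasonable window and be kept after the repair.
- PP could remove some of these values through major deviations. The Protocol Deviation Plan that defines them is not among the documents, so this can be neither credited nor ruled out.
- Setting values to missing has its own cost. The MMRM then borrows from earlier on-drug visits, which moves the Day 56 estimate towards what would have been seen had participants continued.

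None of this supplies a last-dose rule for the primary analysis.

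**Conclusion.** The concern holds as a mismatch between the strategy named and the data rule given. For stopped or interrupted drug, SAP 3.4.1 does not implement a while-on-treatment analysis, and LDL-C sampled after the last dose can enter the primary MMRM, including as the Day 56 value.

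The size is probably small: about 1.1 points of 30 for each fully washed-out value at 27 per arm, with power above 97% for two. This rests on the plan's effect and SD, a two-sample approximation to the MMRM, and assumed offset and visit gaps. The documents give no LDL-C offset time, so the true effect may be near zero.

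A reader might infer that the primary test is invalid or prone to false positives. The documents do not support that, because off-drug values in an active arm pull its estimate towards placebo. The reason to act is that the primary estimate should be the one described and the choice of values should not be left open. Confidence is high on the text and low on the size.

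**What to change.** Before unblinding, amend the SAP as follows.

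1. In all mITT participants, withdrawn or not, exclude from the primary while-on-treatment analysis any Day 14, 28, 56 or ET LDL-C sampled more than a stated number of days after the last dose taken before that sample. Apply this before visit mapping and justify the window from the sponsor's own LDL-C offset data. Protocol 5.5.3 has drug taken after blood sampling on visit days, so the window must allow for the normal interval since the previous dose.
2. Give the non-adherence event a date: the last dose for those who stop and, for sporadic under-dosing, the first visit at which cumulative tablet-count compliance is below 75%.
3. Refer the 75% test to the SAP 3.3.7 formula and define end of treatment date for that test so that it is not the last-dose date. Otherwise a participant who stops at Day 28 with ET at Day 56 scores 28/28 = 100% instead of 28/56 = 50%, and the test cannot detect early stopping.
4. Keep an analysis of all collected values as supportive, and run Sensitivity Analysis 1 on the data after the cut, so that its placebo-based imputation tests the added reliance on MAR. State that the MMRM Day 56 estimate after the cut leans towards continued treatment.

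The cost is a few lines of text, minor programming and a few more missing values. With two active-arm values removed (25 against 27), SE = 25 × √(1/25 + 1/27) = 6.94 instead of 6.80, and power is 98.9%. Interruption dates must be confirmed as collected, because protocol 5.5.4 describes tablet counts; if they are not, tablet counts between visits are the fallback. This is data handling only and changes no clinical management.

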9.2.1.1 Primary efficacy analysis

The primary efficacy analysis of the percent change from Day 1 to Day 56 in LDL-C will be performed using a mixed model for repeated measures approach. The analysis will include fixed effects for treatment, visit, and treatment-by-visit interaction, along with a covariate of the Baseline value. The Restricted Maximum Likelihood estimation approach will be used with an unstructured covariance matrix. The least squares means, standard errors, and 2-sided 95% confidence intervals for each treatment group and for the pairwise comparisons of each dose of obicetrapib to the placebo group will be provided. In order to maintain the overall alpha level on the primary endpoint, the hypothesis testing will be performed sequentially at the 2-sided alpha=0.05 significance level. The first comparison will be the 10 mg obicetrapib group versus

placebo; if significant, comparison of the 5 mg obicetrapib group versus placebo will be performed, followed by the 2.5 mg obicetrapib group versus placebo. Hypothesis testing will proceed in this hierarchical step-down fashion until a comparison is not significant. At that point, all remaining sequential tests will be deemed not significant. Missing data will be imputed using multiple imputation methodology. Results will be combined using Rubin's method. Full details of the model and imputation will be provided in the SAP.

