9.2.5 Sample Size Determination

A sample size of at least 100 evaluable participants (i.e., 25 participants per treatment group) will provide >90% power to detect a 30% difference in LDL-C reduction at Day 56 (SD of 25%) for each of the obicetrapib groups compared to the placebo group at a 2-sided significance level of 0.05.

The sample size for this study was determined in order to provide sufficient power for the analyses of the primary efficacy endpoint described in Section 7. Therefore, assuming a dropout rate of approximately 7%, an estimated enrollment target of approximately 108 participants (i.e., 27 participants per treatment group) is planned for this study. This sample size will also contribute sufficient participant exposure and safety data.

Participants will be stratified according to their Screening Visit (Visit 1) LDL-C levels (≥100 or <100 mg/dL).

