3.4.1 Primary Efficacy Endpoint

Primary Analysis

The primary efficacy endpoint is the percent change from Day 1 to Day 56 in LDL-C (as determined by approach 1) for each obicetrapib group compared to the placebo group. The percent change will be calculated from Day 1 (Baseline) to each measurement taken at Day 14, Day 28, and Day 56.

The mean percent change from Day 1 to Day 56 in LDL-C for each treatment is defined mathematically as μ_j , where j stands for jth treatment (j=0,1,2,3) and the subscripts 0, 1, 2, and 3 refer to the placebo, Obicetrapib 10 mg, 5 mg, and 2.5 mg group, respectively. The hypotheses

testing to the difference in the mean percent change in LDL-C from Day 1 to Day 56 between the j^{th} obicetrapib group and the placebo group is then defined statistically as following:

$$H_0: \mu_j - \mu_0 = 0, H_1: \mu_j - \mu_0 \neq 0, \text{ where } j = 1, 2, 3$$

The primary efficacy analysis of the percent change from Day 1 to Day 56 in LDL-C will be performed using a mixed model for repeated measure (MMRM) approach. The analysis will include fixed effects for treatment, visit, and treatment-by-visit interaction, along with a covariate of the Baseline value as a continuous covariate. It is to note that randomization was stratified by categories of LDL-C value (≥ 100 or < 100 mg/dL) only to ensure similar distribution of LDL-C values across all treatment. However, the MMRM model will include the original scale of the LDL-C value as a continuous covariate, not categorical.

The Restricted Maximum Likelihood estimation approach will be used with an unstructured covariance matrix. The least squares means, standard errors, and 2-sided 95% confidence intervals for each treatment group and for the pairwise comparisons of each dose of obicetrapib to the placebo group will be provided. The least squares means for the pairwise comparison and its standard error will be used for the hypothesis testing. The ratio of estimate to standard error will be approximately t distributed. The null hypothesis of no treatment effect will be rejected if the p-value, the probability of obtaining the observed or more extreme value of t statistic under the null hypothesis, is less than or equal to 0.05.

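### The primary MMRM shares one Baseline LDL-C slope across Days 14, 28 and 56; a Baseline-by-visit term could recover up to about 3% of the Day 56 standard error at almost no cost

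*SAP*

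**What the plan says.** Protocol and SAP agree on the mean model. Protocol 9.2.1.1: "The analysis will include fixed effects for treatment, visit, and treatment-by-visit interaction, along with a covariate of the Baseline value". SAP 3.4.1 uses the same terms and adds that Baseline enters on its original scale, "along with a covariate of the Baseline value as a continuous covariate". The example code is "model PCHG = TREATMENT BASE VISIT TREATMENT*VISIT / solution cl", and BASE is not in the CLASS statement. No Baseline-by-visit term appears in either document.

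On the covariance side the SAP is unrestrictive: "The Restricted Maximum Likelihood estimation approach will be used with an unstructured covariance matrix". Three post-Baseline visits enter: "The MMRM approach will include all available assessments of percent change in LDL-C from Baseline to Day 14, Day 28, and Day 56". The endpoint and the fixed sequence of dose comparisons concern Day 56 only.

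The SAP comments on Baseline only to explain why it is continuous rather than split at the stratification cut-off. It gives no reason for a common slope. Sensitivity Analysis 2 is an ANCOVA of Day 56 percent change on treatment and Baseline, so it has its own Day 56 slope. Sensitivity Analysis 1 and Sections 3.4.2 and 3.4.3 reuse the primary MMRM or a similar one.

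**The concern.** Percent change has Baseline in its denominator. If later LDL-C values correlate less with Baseline than earlier ones do, the slope of percent change on Baseline steepens from Day 14 to Day 56. A single slope is then too shallow at Day 56, and a chance difference in Baseline LDL-C between arms of about 25 is only partly adjusted away there.

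Two things are at stake. One is a little precision in the Day 56 contrasts. The other is how the sensitivity analyses read: a gap between the primary MMRM and the Day 56 ANCOVA would normally be put down to missing data, but here part of it could come from the slope restriction.

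**Working it through.** **1. The plan's own figure.** Protocol 9.2.5 states "A sample size of at least 100 evaluable participants (i.e., 25 participants per treatment group" and "will provide >90% power to detect a 30% difference in LDL-C reduction at Day 56 (SD of 25" percent).
- SE = 25 × √(2/25) = 7.07 points, and 30/7.07 = 4.24.
- Power = Φ(4.24 − 1.96) = 98.9%. By noncentral t it is 98.6% on 48 df and 98.7% on 96 df (four arms pooled).
- Dropout: 25/0.93 = 26.9, so 27 per arm and 108 in total.

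The stated figures reproduce.

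**2. What a common slope does.** Let b14, b28 and b56 be the true visit slopes. With complete data:
- Common slope: b_c = Σ w·b, with weights w = M⁻¹1 / (1′M⁻¹1), where M is the residual covariance including the slope misfit.
- Day 56 residual variance = S² + (b56 − b_c)² × Var(BASE), where S² is the variance with a visit-specific slope.
- SE ratio = √[1 + (b56 − b_c)² × Var(BASE) / S²].

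**3. Falling correlation (assumed).** Assumptions: lognormal LDL-C, log SD 0.25, log measurement SD 0.08, median 105 mg/dL, exponential decay in time, no treatment effect. The log variance is 0.25² + 0.08² = 0.0689, so SD(BASE) = 105 × e^(0.0689/2) × √(e^0.0689 − 1) = 29.0 mg/dL.

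| 4-week correlation | Slopes, Days 14 / 28 / 56 | Weights | b_c | SD at Day 56 | S | SE ratio |
|---|---|---|---|---|---|---|
| 0.95 | −0.104 / −0.124 / −0.163 | 0.51 / 0.30 / 0.19 | −0.121 | 16.1 | 15.4 | 1.003 |
| 0.85 | −0.147 / −0.205 / −0.310 | 0.62 / 0.23 / 0.15 | −0.185 | 22.6 | 20.7 | 1.015 |
| 0.70 | −0.215 / −0.327 / −0.502 | 0.64 / 0.18 / 0.18 | −0.287 | 29.3 | 25.4 | 1.030 |

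Middle row: S = √(22.6² − (0.310 × 29.0)²) = 20.7. The misfit is (0.310 − 0.185) × 29.0 = 3.6, so the ratio is √(1 + (3.6/20.7)²) = 1.015. The earlier visits carry 81 to 85% of the slope weight. The planning SD of 25 lies between the lower two rows. Finite-sample simulation (25 per arm, 3000 runs per setting) gave 0–0.3%, 1.0–1.3% and 2.3–2.8%.

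**4. Other covariance patterns (also assumed).** Here 25 is the unadjusted Day 56 SD, with 25 per arm. Example: equal visit SDs, Baseline correlations −0.2/−0.3/−0.4, residual between-visit correlation 0.5.
- Slopes per Baseline SD are −5, −7.5 and −10. Weights are 0.28/0.32/0.39, so b_c = −7.78.
- S = 25 × √(1 − 0.16) = 22.91. With the common slope it is √(22.91² + 2.22²) = 23.02.
- SE is 6.48 with visit-specific slopes and 6.51 with a common slope (0.5%).

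Other patterns:
- Baseline correlation −0.3 at every visit, equal SDs: SE 6.75 either way, no loss.
- Correlations 0/0/−0.4, equal SDs: 6.48 versus 6.59–6.68 (1.7–3.0%).
- Correlations 0/0/−0.4, visit SDs 18/20/25, residual correlation 0.7: 6.48 versus 7.06 (9%). This extreme needs Baseline to predict Day 56 and neither earlier visit.

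Across all patterns tried, Day 56's weight in the common slope ran from −0.10 to 0.93.

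**5. Power.** Applying the largest simulated loss in step 3 to the planning SE gives 7.07 × 1.028 = 7.27 and 98.3% power (96 df), against 98.7%. At 1.3% it is 98.6%. In the 9% extreme the SE of 7.06 is still no larger than the planning SE of 7.07.

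**6. With dropout.** REML simulation, 27 per arm, 7% dropout, mean SE at Day 56:

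| Baseline correlations | Common slope | BASE*VISIT | Day 56 ANCOVA |
|---|---|---|---|
| −0.3 / −0.3 / −0.3 | 6.63 | 6.64 | 6.74 |
| −0.2 / −0.3 / −0.4 | 6.42 | 6.38 | 6.49 |
| 0 / 0 / −0.4 | 6.61 | 6.39 | 6.49 |

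Bias was at most 0.2 points, within simulation error. Power at 30 points was 98.9–99.6% with the common slope and 99.6–99.8% with BASE*VISIT.

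**7. Gap between the primary analysis and Sensitivity Analysis 2, no missing data.** With BASE*VISIT every visit has the same regressors, so the MMRM and the ANCOVA give the same Day 56 point estimate. With a common slope they differ by (b56 − b_c) times the Baseline difference between arms. Ignoring stratification, that difference has SD 29.0 × √(2/25) = 8.2 mg/dL. The gap then has SD 0.125 × 8.2 = 1.0 point at correlation 0.85 and 0.215 × 8.2 = 1.8 points at 0.70. A simulation with assumed dose effects gave an average gap of 0.6 to 1.1 points in size (95th percentile 1.8 to 3.0) at those settings.

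**The case against.** The best defence is that this is a modelling preference. Text, code and protocol agree. Randomization, stratified on Screening LDL-C, keeps the contrast unbiased and limits Baseline imbalance. The trial's decision does not turn on a 3% change in a standard error. Participants are on an unchanged statin dose, so marked drift over eight weeks is not obvious. Sensitivity Analysis 2 already uses a Day 56 slope. All of this stands, and it is why the point is minor.

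A reader might infer more than the documents support:

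- **That the Day 56 contrast is biased or the trial underpowered.** Neither holds (steps 5 and 6).
- **That the common slope is, as a fact, driven mostly by the earlier visits and always loses precision.** The documents give no Baseline SD, no Baseline correlation by visit and no between-visit correlation. Under falling correlation the earlier visits do dominate. Under other patterns Day 56 can carry most of the weight, and with equal slopes and visit SDs the loss is zero.
- **That the primary model is less precise than its own ANCOVA.** With the planned dropout the MMRM also uses earlier visits of participants without Day 56 data. In step 6 the common-slope model beat the ANCOVA in two of three settings and lost only when Baseline predicted Day 56 alone.
- **That every lipid endpoint loses the same amount.** Sections 3.4.2 and 3.4.3 use similar models, but only LDL-C was examined.

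The defence does not supply a reason to keep the restriction. The SAP leaves the covariance unstructured and offers no argument for constraining the Baseline slope.

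**Conclusion.** The point holds as a cheap improvement. The primary MMRM constrains the Baseline slope to be equal at three visits when only Day 56 is tested. If the correlation with Baseline falls over time, the Day 56 SE is about 0 to 3% larger than necessary. If the slopes are equal, there is no loss. The 9% case is an artificial extreme and should not be quoted as the expected size.

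There is no bias, and planned power remains about 98% or more. The better reason to act is interpretive: with complete data the primary MMRM and Sensitivity Analysis 2 should agree at Day 56, and as written they need not.

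The size rests on assumed variances and correlations, since the documents give only the planning SD of 25 for Day 56.

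**What to change.** Before database lock, while the SAP can still be finalized:

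- In SAP 3.4.1, change the MODEL statement to PCHG = TREATMENT BASE VISIT TREATMENT\*VISIT BASE\*VISIT, and add the Baseline-by-visit interaction to the text.
- Carry the same term into the MMRM of Sensitivity Analysis 1 and the models in 3.4.2 and 3.4.3.
- Record the added term in SAP Section 5, because Protocol 9.2.1.1 lists the fixed effects without it.

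The cost is two more fixed-effect parameters per model, and about 0.01 on the SE if the slopes are in fact equal (6.64 versus 6.63 in step 6). No data collection, sample size or testing order changes.
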